Efficacy assessments	
Detection of SARS-CoV-2 serum functional antibodiesDetection of SARS-CoV-2 specific T-cells
Key safety assessments	
Patients developing COVID-19
Data analysis	The primary analysis will not use any statistical testing or modelling. The absolute numbers and the proportion of participants achieving seroconversion within each cohort will be calculated. It will be augmented by a (descriptive) 95% confidence interval (exact Clopper-Pearson). All secondary endpoints will be summarized descriptively as frequencies and percentages, or, for continuous data, mean, standard deviation, median, minimum, and maximum will be presented.
Key words	COVID-19, SARS-CoV-2, RNA vaccine, siponimod, secondary progressive multiple sclerosis

1 Introduction

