9.1.1.1 Replacement policy

Patients failing the screening visit (detectable levels of SARS-CoV-2 serum functional antibodies) will be replaced. Patients successfully screened who do not receive a mod-RNA SARS-CoV-2 vaccination according to EU SmPC within 1 month after screening will be excluded from the study and replaced unless the patient is currently not eligible for SARS-CoV-2 vaccination by local regulation. In this case, the Novartis Medical Advisor should be contacted to discuss further proceeding including re-evaluation of anti-SARS-CoV-2 antibody level and PCR test. Patients developing symptoms of COVID-19 or have a SARS-CoV-2 infection (positive test result) between screening and first vaccination will be excluded from the study and will be replaced.

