#### **2.1.1 General definitions**

##### **Study treatments**

The modRNA vaccine and the treatment for MS are defined both as study treatments. More specifically, the MS treatment is established as study treatment from the time of informed consent.

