## **2.2 Analysis sets**

For all analysis sets, participants will be analyzed according to the study treatment(s) received.

The safety analysis set (SAF) will include all participants that received any study drug.

The efficacy analysis set will include all participants who have a valid primary endpoint (i. e. determination of functional antibodies to SARS-CoV-2 at Visit 2 / Week 1) plus those who failed to receive their second dose of vaccine for whatever reason.

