## 2.7 Analysis of secondary efficacy objective(s)

### 2.7.1 Secondary endpoints

The secondary endpoints are analyzed descriptively within each cohort. The efficacy analysis set is used for all analyses of the secondary parameters.

The semiquantitative SARS-CoV-2 serum functional antibody titer (percent inhibition) is summarized by arithmetic mean, standard deviation, minimum, median and maximum by visit. A boxplot graph will be presented.

The SARS-CoV-2 serum functional antibody titer is summarized by geometric mean, geometric coefficient of variation (CV) and 95% confidence intervals for the (geometric) mean. The Visits Screening, Visit 1/Week 1, Visit 2 /Month 1 and Visit3 /Month 6 are displayed separately in this summary table and a boxplot graph with logarithmic y-axis (log base 10).

The same summary table and boxplot will be provided for the following secondary parameters:

- a) Qualitative and quantitative result of IFNg towards SARS-CoV-2 and towards coronaviridae
- b) Qualitative and quantitative result of IL-2 towards SARS-CoV-2 and towards coronaviridae
- c) Combined response in qualitative INFg or IL-s towards SARS-CoV-2 and towards coronaviridae, i. e. reactive to INFg or IL-2 or to both.
- d) Cell viability, CD3 lymphocytes, CD4 and CD8 cells, percentage of CD4+ and CD8+ cell in peripheral blood mononuclear cells

The percent inhibition values for INFg at screening will be displayed for the subset of patients who are reactive at Week 1 versus non-reactive. The same analysis is provided for IL-2.

All other laboratory data (e. g. number of basal/background spots, spots, quality, comments, mutations) are listed only.

The MS activity is measured by relapses. The crude annual relapse rate until end of study and underlying sums (of relapses and patient-years) will be presented.

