## **2.8 Safety analyses**

All safety analyses are presented for the Safety Set (SAF). Descriptive statistics are presented within study treatment groups (cohorts 1-3).

It should be mentioned that the follow-up analysis amends all analyses of adverse events. The CSR is planned to be finalized after this follow-up analysis.

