### **2.8.1 Adverse events (AEs)**

According to the CSP all adverse events starting in the on-treatment period, i. e. the treatment emergent AEs, are analyzed.

The on-treatment period lasts from the date of first administration of study treatment after informed consent to 30 days after the month 12 COVID-19 follow-up call.

The number (and percentage) of subjects with treatment-emergent adverse events will be summarized in the following ways:

- by treatment group (cohort 1-3), primary system organ class and preferred term.
- by treatment group (cohort 1-3), primary system organ class, preferred term and maximum severity

A subject with multiple AEs within a MedDRA primary system organ class is only counted once towards the total of the primary system organ class.

A subject with multiple AEs within a preferred term is only counted once towards the total of the preferred term class.

Separate summaries will be provided for study medication related AEs, death, SAEs, AEs leading to discontinuation and adverse events leading to dose adjustment.

The absolute and relative frequency of COVID-19 infections is presented.

Deaths and serious adverse events are listed in addition.

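### COVID-19 is planned only as a crude percentage of the safety set per cohort, with no follow-up time and no split at the second dose

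*SAP*

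**What the plan says.** The protocol summary gives a single entry under key safety assessments: "Patients developing COVID-19". Protocol section 3 schedules a call 50 to 54 weeks after completed vaccination to ask about confirmed COVID-19, and Table 8-1 collects adverse events at every visit and contact.

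SAP 2.8.1 plans one summary: "The absolute and relative frequency of COVID-19 infections is presented". SAP 2.8 places it in the safety set, by cohort. SAP 2.8.1.1 adds a listing of COVID-19-related adverse events. On the set itself, SAP 2.2 says: "The safety analysis set (SAF) will include all participants that received any study drug".

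The observation window is defined. SAP 2.8.1 and 5.2 run it from the first study treatment after consent to 30 days after the Month 12 call or, if there is no call, to 30 days after the last visit. No rule says how that shorter window enters the COVID-19 denominator.

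Other outcomes get more. For relapses, SAP 2.7.1 gives a crude annual rate and says that the "underlying sums (of relapses and patient-years) will be presented". For deaths, SAP 2.8.2 gives a 95% confidence interval.

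**The concern.** In a vaccination study, a COVID-19 percentage by cohort is likely to be read as infection after vaccination under each treatment strategy. The planned figure is not quite that, for two reasons. It pools infections between dose 1 and dose 2 with those after the full cycle. It also gives a patient who was last seen at Month 6 and never reached again the same weight as a patient followed to Month 12. Any infection in the unobserved time is missed while the denominator stays whole, so the percentage is pulled down. If loss to follow-up differs between cohorts, the pull differs too.

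A smaller matter is the period before dose 1. The protocol removes patients infected then, but the SAP's safety-set rule does not carry that over.

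**Working it through.** The documents give no COVID-19 count, no assumed incidence and no number not reached, so there is no planned COVID-19 figure to reproduce. The one design figure used is the cohort size in SAP section 3: 20 × 1.1 = 22.

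**1. Share of the window before the cycle takes effect.** Inputs:
- Screening 3 to 30 days before dose 1 (Protocol Table 8-1), taking consent at screening.
- Dose interval 3 or 4 weeks, that is 21 or 28 days (Protocol 1.1).
- Call 50 to 54 weeks after dose 2, that is 350 to 378 days (Protocol section 3).
- Window closes 30 days after the call (SAP 5.2).
- A 7-day lag after dose 2, which is an assumption.

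Share = (interval + 7) / (screening + interval + call + 30).
- Smallest: (21 + 7) / (30 + 21 + 378 + 30) = 28/459 = 6.1%.
- Largest: (28 + 7) / (3 + 28 + 350 + 30) = 35/411 = 8.5%.

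For untreated cohort 3 patients, whose window starts at dose 1, the same formula without screening gives 28/429 = 6.5% to 35/408 = 8.6%. The share is therefore about 6% to 9%.

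**2. Time lost when the call is missing.** Both ends of the window carry the same 30 days. For a patient last seen at Month 6 (week 25 to 27), it shortens by 50 − 27 = 23 to 54 − 25 = 29 weeks. The patient still counts as one in the denominator.

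**3. Effect on the percentage.** Assume N = 22, m patients not reached, and x infections, all among those reached. The planned figure is x/N, the figure among those reached is x/(N − m), and the bound if every unreached patient was infected is (x + m)/N.

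| x | m | x/22 | x/(22 − m) | (x + m)/22 |
|---|---|---|---|---|
| 1 | 2 | 4.5% | 5.0% | 13.6% |
| 3 | 2 | 13.6% | 15.0% | 22.7% |
| 5 | 2 | 22.7% | 25.0% | 31.8% |
| 3 | 4 | 13.6% | 16.7% | 31.8% |

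With m = 2 the planned figure is 20/22 = 0.91 of the figure among those reached, about 9% lower in relative terms. The exact 95% interval for 3/22 is 2.9% to 34.9%.

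**4. The same case as a rate.** Take 3 infections after dose 2, 20 patients followed for 365 days, and 2 last asked on day 182. Patient-years are (20 × 365 + 2 × 182)/365.25 = 20.98, and the rate is 3/20.98 = 14.3 per 100 patient-years. If the two were last asked on day 8, it is 3/20.03 = 15.0. Crediting all 22 with full follow-up gives 3/21.98 = 13.6. Time is not stopped at infection here; stopping it would raise each rate.

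**5. Infections before dose 1.** The passages side by side:
- Protocol 9.1.1.1: patients who develop symptoms or test positive "between screening and first vaccination will be excluded from the study and will be replaced".
- SAP 2.1.1 classes a patient without an mRNA vaccination as a screening failure, and Protocol 8.3.2 keeps little data on screening failures unless a serious event occurs.
- SAP 2.1.1 also says that "the MS treatment is established as study treatment from the time of informed consent", so a patient on MS treatment meets the safety-set definition before any vaccination.
- SAP 5.4 removes from the safety set only patients without consent or without any study treatment. A missing first vaccination excludes from the efficacy set only.
- SAP 5.2 starts the window at consent for cohort 1 and for cohort 3 patients on a DMT, but at first vaccination for untreated cohort 3 patients.

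The intent to remove these patients is clear. The safety-set rule does not state it.

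**The case against.** The strongest reply is that the summary matches the endpoint. Protocol Table 2-1 lists patients with clinically confirmed COVID-19 under an objective of describing safety. That is a count of patients, not an estimate of protection after a full cycle, and no formal comparison between cohorts is planned. Cases are also listed, so with about 20 patients per cohort a reader can look at each one. SAP 2.3.1 tabulates missed visits and drop-outs with reasons. A patient lost late still contributes every infection recorded up to that point. This stands as a reason to keep the planned frequency, but it does not put follow-up time into the percentage.

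Three stronger readings are tempting, and the documents do not support them:
- *Infections before vaccination are counted.* Protocol 9.1.1.1, Protocol 8.3.2 and SAP 2.1.1 together point the other way. The footnote to the efficacy set in SAP 2.2 also reports that all patients received their second dose. What remains is a gap between that intent and the safety-set rule.
- *There is no counting window.* There is one, in SAP 2.8.1 and 5.2. It is not tied to completed vaccination, and it is not used as a denominator.
- *Unreached patients are declared uninfected.* The SAP does not say this, and SAP 5.1 imputes nothing beyond partial dates. That they weigh as non-events for the unobserved time is an arithmetic result of a crude percentage.

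**Conclusion.** The point holds in a limited form. The only named key safety assessment is summarised without follow-up time and without separating infections before and after the second dose. As a 12-month figure the percentage is biased low whenever patients are not reached, provided they had some risk of infection in the unobserved time.

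The size is modest: 13.6% against 15.0% with 3 infections and 2 of 22 not reached, or against 16.7% with 4 not reached. Both differences are small beside the interval of 2.9% to 34.9%. The span from dose 1 to 7 days after dose 2 is about 6% to 9% of the window. The numbers of infections and of patients not reached, and the 7-day lag, are assumptions. Nothing here touches the primary endpoint.

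**What to change.** In SAP 2.8.1, keep the planned frequency and add by cohort:
- (a) the number of infections before and after the second dose;
- (b) for infections after the second dose, the patient-years from that dose to first infection or last COVID-19 inquiry, and the rate with an exact 95% confidence interval (SAP 2.7.1 already does this for relapses, without an interval);
- (c) the number of patients not reached at the Month 12 call.

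Reconcile the safety-set rule in SAP 2.2 and 5.4 with Protocol 9.1.1.1 and SAP 2.1.1, so that the status of a patient infected before dose 1 is explicit.

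The cost is some SAP wording and one more table with small counts, built from vaccination and event dates already collected. The SAP history places its latest revision after final data review, so the table should be labelled as added at that stage.

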#### **2.8.1.1 Adverse events of special interest / grouping of AEs**

Adverse events related to COVID-19 are listed.

## **2.8.2 Deaths**

Deaths are listed. A frequency table with absolute numbers, percentages and 95% confidence interval is presented.

## **2.8.3 Laboratory data**

Not applicable.

## **2.8.4 Other safety data**

### **2.8.4.1 Physical examination**

Clinically significant findings which were not present at screening but at any later visits are displayed by a frequency table.

### **2.8.4.2 Vital signs**

The changes from screening to Visit 1/Week 1, to Visit 2/Month 1, to Visit 3/Months 6 as well as differences between last and first value are displayed for pulse, systolic/diastolic blood pressure and body weight.

## **2.9 Pharmacokinetic endpoints**

Not applicable.

## **2.10 PD and PK/PD analyses**

Not applicable.

## **2.11 Patient-reported outcomes**

Not applicable.

## **2.12 Biomarkers**

Not applicable.

## **2.13 Other Exploratory analyses**

Not applicable.

## **2.14 Interim analysis**

See section 1.1 Study design.

## **3 Sample size calculation**

The sample size of 20 participants per arm is selected based on need for early availability of results for the current covid-19 pandemic and the feasibility to recruit sufficient participants from AMASIA and PANGAEA 2.0 EVOLUTION. This sample size of 20 subjects will provide estimates of proportion responded with margin of error (half-width of a 95% confidence interval) of 20.1%, 19%, and 17.5% corresponding to response rates of 70%, 75%, and 80%, respectively. Adjusting for 10%

drop-out, 22 subjects will be enrolled in each arm. In case of fast recruitment the sponsor is allowed to increase sample size in each arm by up to 10 additional patients to support the generation of meaningful data in a larger sample size.

## **4 Change to protocol specified analyses**

The definition for the Efficacy analysis Set was adapted to avoid that non-missing secondary endpoints would be excluded from the efficacy analysis set. For the rate of seroconversion (primary parameter) the patients with missing data are already excluded from the denominator.

## **5 Appendix**

### **5.1 Imputation rules**

No imputations will be done except:

If differences between dates are calculated, partial dates are replaced by 15/6 for days/month. If negative date differences result from this replacement, the value is set to 0.

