This is a three cohort, multicenter, open-label, prospective study of 60 (optional increase to 90) MS patients currently treated with siponimod or a first-line DMT (as per EU SmPC) or without MS treatment planning to undergo a SARS-CoV-2 modRNA vaccination as part of clinical routine and according to the respective EU SmPC. For each participant, total expected duration of the trial is 56-60 weeks.

- The first cohort will be participants not interrupting their current siponimod therapy for the purpose of a SARS-CoV-2 modRNA vaccination. In case of a booster vaccination, patients in this cohort may also undergo a treatment break which is also covered by the EU SmPC.
- The second cohort will be participants interrupting their current siponimod therapy for the purpose of a SARS-CoV-2 modRNA vaccination (treatment interruption of about 2-3 months).

- The third cohort will be participants receiving modRNA vaccine while on treatment with first-line DMTs (dimethylfumarate, glatirameracetate, interferons, teriflunomide) or no current treatment in clinical routine.

The interventional part of AMA-VACC is limited to the collection of blood samples at specified time-points to analyze levels of SARS-CoV-2 specific antibodies and T-cells as response to the modRNA vaccination in clinical routine.

There are 3 study periods:

1. Screening period:

Participants enter a screening period of up to 1 month to assess eligibility requirements including a blood draw and assessment of SARS-CoV-2 specific antibodies at baseline to exclude any prior exposure to the virus or a vaccination. In case the patient is not eligible for SARS-CoV-2 vaccination by local regulation within this time, the Novartis Medical Advisor should be contacted to discuss further proceeding including re-evaluation of anti-SARS-CoV-2 antibody level and PCR test. Furthermore, a SARS-CoV-2 PCR test will be performed at screening to exclude current COVID-19 infection. In case of a positive test result, the patient has to go into quarantine immediately. Patients are only allowed to continue within the study and receive SARS-CoV-2 vaccination once they received a negative PCR test result.

2. Vaccination period

Patients are vaccinated with a complete cycle of modRNA based SARS-CoV-2 vaccine at the discretion of the treating physician outside the study as part of clinical routine.

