5.1 Inclusion criteria

Participants eligible for inclusion in this study must meet **all** of the following criteria:

1. Signed informed consent must be obtained prior to participation in the study.
2. One of the following MS treatments as part of clinical routine (according to respective SmPC):
 - a. **Cohort 1:** Siponimod treatment according to EU SmPC **without interrupting daily dosing** for the purpose of vaccination with SARS-CoV-2 modRNA
 - b. **Cohort 2:** Siponimod treatment according to EU SmPC **interrupting daily dosing** for the purpose of vaccination with SARS-CoV-2 modRNA

- c. **Cohort 3:** Dimethylfumarate, glatirameracetate, interferon, teriflunomide as per respective EU SmPC or no current treatment with diagnosis of SPMS or with RRMS at risk to develop SPMS (at the discretion of the treating physician)
3. Planning to receive a SARS-CoV-2 modRNA vaccination as part of clinical routine
4. No change regarding DMT within 4 weeks prior to inclusion to AMA-VACC, i.e. stable on current DMT according to dosing within label, no interruption, start or withdrawal of DMT in this period of time and no planned switch of DMT within following 2 months
5. Patients willing and eligible to receive a modRNA vaccine against COVID-19 as part of clinical routine

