12.3.4 Supportive analyses

Patient demographics and baseline characteristics among 3 cohorts will be compared in the data analysis. Also the treatment interruption time of the selected cohort 2 patients will be compared to that of other siponimod treated patients in AMASIA interrupting daily dosing as per label for the purpose of vaccination with SARS-CoV-2 modRNA as part of clinical routine. If major imbalance is discovered, the study results will be interpreted with more caution and post-hoc supportive analyses may be conducted to adjust for the imbalance.

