## **2.4 Treatments (study treatment, rescue medication, concomitant therapies, compliance)**

### **2.4.1 Study treatment / compliance**

The absolute and relative frequency of performed study visits and performed vaccinations are presented. Sample statistics for the duration of intervals between screening and date of 1st vaccination, date of 1st and 2nd vaccination and date 2nd vaccination to Visit 1/Week 1 are displayed. The interval from the 2nd Vaccination to Visit 1/Week 1, Visit2 /Month 1 and Visit 3/Month 6 are also displayed by sample statistics. Here always the exact date of the respective vaccination is used but not the date of study visit called “Vaccination 1” or “Vaccination 2” which displays the date of phone contact with the patient.

Two types of investigational study drugs are used in this study:

1. Study medication for treatment of MS
2. Study medication for vaccination

The study medication for treatment of MS is displayed by frequencies for type of medication (cohort 3 only), sample statistics for duration of treatment prior to screening (cohort 1 and 3) and frequencies of dose changes, interruptions, or discontinuation until Visit 1, 2, and 3 respectively (cohort1 and 3). For cohort 2 the duration of siponimod interruption (i. e. the time between last dose prior to vaccination and the fist dose after vaccination) is displayed by sample statistics.

The different vaccines are displayed by a frequency table separately for 1st and 2nd vaccination.

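### The partial-date rule in SAP 5.1 ignores other recorded dates, so a missing month can give impossible prior-treatment durations and zero-day siponimod breaks

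*SAP*

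**What the plan says.** SAP 5.1 has a single imputation rule. When differences between dates are calculated, "partial dates are replaced by 15/6 for days/month". It continues: "If negative date differences result from this replacement, the value is set to 0". It sets no limit from the screening date, the vaccination dates or the other end of the interval, and no limit on how much of a date may be missing. No interval becomes missing, and affected values are not counted.

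Two summaries in SAP 2.4.1 depend on dates that may be partial:
- how long patients in cohorts 1 and 3 had been on their MS treatment before screening;
- "For cohort 2 the duration of siponimod interruption", measured from the last dose before vaccination to the first dose after it.

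The same section says that exact vaccination dates are used, but says nothing comparable about DMT start, stop or restart dates.

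Two protocol statements limit what these intervals can be. Inclusion criterion 4 (protocol 5.1) requires "No change regarding DMT within 4 weeks prior to inclusion to AMA-VACC", spelled out as "no interruption, start or withdrawal of DMT in this period of time". Protocol section 3 describes cohort 2 by a "treatment interruption of about 2-3 months". Protocol 12.3.4 adds that "the treatment interruption time of the selected cohort 2 patients will be compared" with that of patients in the parallel siponimod study AMASIA.

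**The concern.** A negative interval after imputation shows that the substituted date is wrong. Setting it to 0 removes that evidence and puts a real-looking number in the table. A reader cannot tell such a 0 from a patient who truly started treatment on the day of screening, or from a cohort 2 patient who took no break.

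Break length describes what cohort 2 actually did, and the protocol plans to compare it externally. With about 20 patients per cohort, one false 0 fixes the reported minimum and visibly moves the mean.

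**Working it through.** The plan states no figure for this point, so the check applies the rule by date arithmetic.

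**Inputs**
- Rule: missing day becomes 15; missing day and month become 15 June of the stated year; result = max(0, difference) (SAP 5.1).
- Shortest eligible DMT duration: 4 weeks = 28 days (protocol 5.1, criterion 4). I take screening as the inclusion date, because Table 8-1 places the eligibility check there. The limit does not apply to untreated cohort 3 patients.
- Break length: the label text quoted in protocol 1.1 gives 1 week before to 4 weeks after vaccination, with 3 or 4 weeks between doses. That is 7 + 21 + 28 = 56 days or 7 + 28 + 28 = 63 days.
- Screening period (assumption; the documents give no dates): 20 April to 25 September 2021, which is 159 calendar dates. The start is the date of the SAP draft made before the first patient's first visit; the end is the release of Amendment 2, which stops recruitment.

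**Prior treatment, start known only as 2021**

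The rule gives max(0, screening − 15 June 2021). The possible range is 28 days to (screening − 1 January 2021).

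| Screening | Rule gives | Possible |
|---|---|---|
| 15 May 2021 | 0 | 28 to 134 |
| 1 July 2021 | 16 | 28 to 181 |
| 12 July 2021 | 27 | 28 to 192 |
| 13 July 2021 | 28 | 28 to 193 |

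Of the 159 assumed screening dates, 57 (20 April to 15 June) give 0 and 84 (20 April to 12 July) give less than 28. These are counts of dates, not of patients.

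**Cohort 2 break, true length 63 days in each example**

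| Stop | Restart | Raw difference | Reported |
|---|---|---|---|
| 20 April, known as 2021 | 22 June, known as 2021 | 15 June − 15 June = 0 | 0 |
| 12 April, known as 2021 | 14 June, exact | 14 June − 15 June = −1 | 0 |
| 1 July, exact | 2 September, known as 2021 | 15 June − 1 July = −16 | 0 |

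In the first row the substitution alone produces the 0. In the other two the floor does.

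**Weight of one false value.** One 0 in place of 63 among 20 patients moves the mean by 63/20 = 3.15 days and makes the minimum 0.

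**Where the problem stops**
- Only the day missing, start date: no zero or negative value arises for an eligible patient. The smallest result is 14 days (start 1 April, screening 29 April, true value 28).
- Only the day missing, break dates: never 0. True breaks of 56 to 92 days come out between 30 and 122 days.
- Year-only start in an earlier year: stays above 28 days but is imprecise. A start in 2020 with screening on 1 May 2021 gives 320 days; 121 to 486 are possible.

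**The case against.** The strongest reply is that the triggering data should be rare. Protocol Table 8-1 records MS medication at screening, at both vaccination contacts and at every visit. Protocol 8.1 asks for prescriptions and lot numbers, 11.2 has missing values queried, and 11.3 has monitors check prescription records. A cohort 2 stop or restart without a month is therefore unlikely. This stands, with one qualification: SAP 5.2 allows for siponimod being interrupted before consent, so not every stop falls under prospective follow-up. A DMT start is historical by nature, but there the zero needs a start in 2021, an unknown month and an early screening date.

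Three stronger readings are tempting, and the documents do not support them.
- *That the rule biases the summaries downward.* Raising a negative value to 0 raises the mean relative to that negative value; any downward shift comes from the 15/6 substitution. The error also runs the other way: two year-only dates either side of New Year give 365 days. Day-15 imputation alone is ordinary two-sided imprecision.
- *That the primary result is at risk.* Seroconversion is derived from antibody results at screening and at the visits (SAP 5.3.1) and reported with Clopper-Pearson intervals (SAP 2.5.2). Neither interval enters.
- *That imputed dates should be made to meet the 28-day criterion, or to place restart after vaccination 2.* That could hide a real eligibility violation or an early restart, which deviation review should find.

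The SAP also does not carry forward the AMASIA comparison from protocol 12.3.4, which narrows the consequence further.

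**Conclusion.** The point holds as a minor one. As written, SAP 5.1 can return values that contradict inclusion criterion 4 or the definition of cohort 2, and the floor disguises them. For a DMT start known only as 2021, the result is 0 days for screening up to 15 June 2021 and under 28 days for screening before 13 July 2021. For the break, two dates known only as the same year always give 0, and one such date can do so.

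This rests on the month being missing in the relevant year and on screening dates in spring to summer 2021, which is an assumption. The number of partial dates is not given, so the actual effect may be nil. What is exposed is the descriptive exposure summaries in SAP 2.4.1 and the interruption-time comparison in protocol 12.3.4.

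**What to change.** In SAP 5.1:
- Delete the replacement of negative differences by 0.
- Restrict each imputed date to the range compatible with its known parts and with recorded dates, for example screening, vaccination 1 and the other end of the interval. State which point of that range is used.
- If no compatible date exists, or if both ends of the break lack a month, set the interval to missing, report the count by cohort, and send the record to data review.
- Do not use eligibility or an assumed restart after vaccination 2 as a limit. List any resulting value that conflicts with them for deviation review.

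The cost is a few sentences and minor programming, and a few intervals may become missing. The SAP history shows a revision after final data review, so affected records can be listed directly. If there are none, no reported result changes.
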